# **11.0** IDENTIFICATION AND SUMMARY OF PROTOCOL DEVIATIONS

Major protocol deviations from entry criteria and treatment compliance will be summarized as far as they can be extracted from numeric or coded study data.

# **12.0** DATA QUALITY ASSURANCE

Accurate and reliable data collection will be ensured by verification and cross check of the CRFs against the investigator's records by the study monitor (source document verification) and by the maintenance of a drug–dispensing log by the investigator. Collected data will be entered into a computer database and subject to electronic and manual quality assurance procedures.

# **13.0** REFERENCES

# 14.0 APPENDICES

# **14.1** APPENDIX A - IMPUTATION ALGORITHM FOR PARTIAL AND MISSING DATES

This section describes missing date imputation methods.

#### **For Adverse Events**

If onset date is completely missing, onset date is set to date of randomization.

If (year is present and month and day are missing) or (year and day are present and month is missing):

- If year = year of randomization, then set month and day to month and day of randomization
- If year < year of randomization, then set month and day to December 31.
- If year > year of randomization, then set month and day to January 1.

If month and year are present and day is missing:

- If year=year of randomization and
  - If month = month of randomization then set day to day of first dose
  - If month < month of first dose then set day to last day of month
  - If month > month of first dose then set day to first day of month
- If year < year of randomization then set day to last day of month
- If year > year of randomization then set day to first day of month

For all other cases, set onset date to date of randomization.

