10.2 Management of Adverse Events

Adverse events will be collected from the time of signing the ICF through 30 days after the last study visit or Early Termination, whichever occurs first. Only Serious adverse events will be collected for subjects who screen fail.

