10.2.3 Documentation

All AEs occurring within the period of observation for the study must be documented in the CRF with the following information, where appropriate. (The period of observation for the study is described in Section 10.2.)

- AE name or term.
- When the AE first occurred (start date and time).
- When the AE stopped (stop date and time or an indication of "ongoing").

- Severity of the AE.
- Seriousness (e.g., hospitalization or death).
- Actions taken.
- Outcome.
- Investigator opinion regarding the AE relationship to the study drug(s).

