#### **10.2** ADVERSE EVENTS

Each AE and SAE term recorded on the case report forms (CRFs) by primary system organ class (SOC) will be mapped to a preferred term using the MedDRA dictionary. The investigator will assess AE severity and relationship to the study treatment.

A treatment emergent adverse event (TEAE) is defined as any AE with an onset date on or after date of randomization, or any ongoing event on the date of first dose that worsens in severity after date of randomization. Only non-serious TEAEs with an onset date prior to date of last dose and serious TEAEs

AXSOME Therapeutics, Inc. AXS-05-MDD-201 SAP CONFIDENTIAL Page 13 of 16 Version 1.0—11 December 2018

with an onset date prior to date of the final visit + 30 days will be tabulated in summary tables. However, all AEs recorded will be listed. For the purpose calculating treatment emergence and inclusion in summary tables, incomplete onset dates will be imputed as detailed in Appendix A.

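### SAP Appendix A dates incomplete AE onsets without using the recorded stop date, so some events that ended in screening are tabulated as treatment-emergent with an onset after their end

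*SAP*

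**What the plan says.** **Collection.** Protocol 10.2 states: "Adverse events will be collected from the time of signing the ICF". Events during screening, which lasts up to 28 days, are therefore in the database. Among the CRF items in Protocol 10.2.3 is one that begins "When the AE stopped (stop date and time or an indication of" and goes on to allow for an ongoing event. The stop date is thus available to the analysis.

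**Use of the imputed date.** SAP 10.2 says that, for treatment emergence and inclusion in the summary tables, "incomplete onset dates will be imputed as detailed in Appendix A". It counts an event as treatment-emergent (a TEAE) from the date of randomization. Protocol 10.1.5 and 12.4.3.1 count from first dose.

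**Imputation rules (SAP Appendix A, adverse events).**
- Nothing known: "If onset date is completely missing, onset date is set to date of randomization".
- Month missing: "If year = year of randomization, then set month and day to month and day of randomization".
- Only the day missing, in the year of randomization: "If month = month of randomization then set day to day of first dose". The next bullet changes the reference date: "If month < month of first dose then set day to last day of month". A third bullet sends months later than the first-dose month to their first day.
- Catch-all: "For all other cases, set onset date to date of randomization".

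**Contrast.** The concomitant medication rules in the same appendix do use the end date. A medication with no start date and an end before randomization is classed as prior.

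**The concern.** Assigning an uncertain onset to the treatment period is a reasonable default when the timing is truly unknown. Here the timing is often known well enough: a stop date before randomization proves that the event was pre-treatment. The AE rules discard that information and produce an onset later than the recorded end.

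Safety and tolerability is the only objective in Protocol Section 5, and the safety analysis is descriptive, so the TEAE tables carry the safety message. SAP 3.0 makes the approved plan binding for all analyses in the study report. Programmers who follow it will create these dates, and correcting them silently would be a deviation. Screening events are plausible, since prohibited psychotropic drugs are washed out before Visit 2 and AEs are reviewed at Visit 2 before any dose.

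**Working it through.** The plan gives no figure on this point, so there is none to reproduce. The check applies the rules as written.

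**Inputs.** Randomization is Day 0 and first dose is the next morning, Day 1 (Schedule of Assessments, footnote h). Screening covers Days -28 to -1. The rules are those of SAP Appendix A and the TEAE window is that of SAP 10.2. Non-serious events are tabulated if onset precedes the last dose, so an onset on Day 0 or Day 1 normally qualifies.

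**1. One subject.** Randomized 15 August, first dose 16 August. The AE stopped on 10 August.

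| Known part of onset | Imputed onset | TEAE in SAP 10.2? | On or after first dose? |
|---|---|---|---|
| Nothing | 15 August | Yes | No |
| Year only | 15 August | Yes | No |
| August, day missing | 16 August | Yes | Yes |

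The imputed onset falls 5, 5 and 6 days after the event ended. Only the last row also meets the first-dose criterion of Protocol 12.4.3.1.

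**2. All screening dates.** Let the onset be k days before randomization (k = 1 to 28) and the stop be any day from onset to Day -1. That gives k possible stops per onset and 28 × 29 / 2 = 406 onset-stop pairs per randomization date. Over 1 July 2018 to 30 June 2019 (365 dates, an assumed span), the total is 365 × 406 = 148,190 pairs. Pairs that become TEAEs with onset after stop:
- Onset wholly missing: 148,190 of 148,190, or 100%.
- Year only: 140,476 of 148,190, or 94.8%. The rest have an onset in the year before randomization and go to 31 December.
- Day missing: 50,778 of 148,190, or 34.3%, if the first matching bullet applies. If a later matching bullet overrides an earlier one, 55,216, or 37.3%.

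As a hand check on the day-missing rule, take randomization on day D of a month (D up to 29, not month end). Onsets in that month have k up to D - 1, which gives D(D - 1)/2 pairs. For D = 15 this is 105/406 = 25.9%; for D = 20 it is 190/406 = 46.8%. These are shares of possible dates, not expected event rates.

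**3. Month end, a separate defect.** Randomized 31 August, first dose 1 September.
- An AE in August meets two bullets. Equality with the randomization month gives day 1, so 1 August, which is 30 days before randomization and outside a 28-day screening window. August is also earlier than September, which gives 31 August.
- An AE in September meets none of the three: it is not August, not earlier than September and not later. The catch-all dates it 31 August, outside its recorded month.

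Twelve of the 365 randomization dates are month ends. Of their 12 × 42 = 504 on-treatment onset days, 334 receive the wrong month. These are the days of every first-dose month except January, 365 - 31 = 334; after a 31 December randomization, the later-year rule correctly gives 1 January. All 334 still count as TEAEs under SAP 10.2.

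**4. Size in a table.** One affected subject adds 1/30 = 3.3 percentage points to a preferred term with 30 subjects per arm. With an assumed 40 per arm it is 1/40 = 2.5 points.

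**The case against.** The best defence is that the effect is small and visible. Start date is a required CRF item, AEs are reviewed at Visit 2, and queries and source verification apply, so a recent event with a known stop and an unknown onset should be rare. The rule is identical in both blinded arms, no formal safety comparison is planned, every AE is listed, and a subject counts once per preferred term. All of this stands as a limit on size. It does not justify the rule: no uncertainty calls for a conservative default once the stop date precedes randomization, and the SAP's own medication rule makes that check.

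A reader might infer more than the documents support:
- *That the month-end fault carries ended screening events into the TEAE tables.* With the bullets read in order, it moves them back to day 1 of the month and out of the tables: 0 of 12 × 406 = 4,872 pairs enter. The effect appears only if a later bullet overrides an earlier one (4,438 of 4,872, or 91%), and the SAP does not say that it does.
- *That the month-end gap loses on-treatment events.* Under SAP 10.2 as written it does not.
- *That all three routes place events on drug.* Only the day-missing rule does. The other two give Day 0, before the first dose.
- *That 3.3 points is the expected shift.* It is about a ceiling. The figure of 30 per arm refers to compliant completers (Protocol 12.2), whereas the Safety Population is everyone dosed, including subjects later replaced.

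**Conclusion.** The stop-date gap is a real defect in a stated rule. A screening AE that stopped before randomization enters the TEAE tables with an onset after its end when the onset is wholly missing or known only to the year of randomization. The same generally holds when it is known only to the month of randomization, with month-end randomizations the exception in listed order. Two of the three routes also depend on SAP 10.2 counting from randomization while the protocol counts from first dose. The month-end overlap and gap are a separate, minor drafting defect: they give conflicting or impossible dates but do not remove on-treatment events from the SAP's tables.

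The size is at most about 3.3 percentage points per preferred term per affected subject, and less if the Safety Population exceeds 30 per arm. The conclusion applies only to AEs with an incomplete onset and a stop date that is known, or known well enough to place it before randomization. The documents do not say how many to expect, and the number is probably small. Because the error is certain where it applies and cheap to remove, the SAP should be corrected before database lock.

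**What to change.** Revise the AE part of SAP Appendix A and the TEAE definition in SAP 10.2 together:

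1. If the stop date, or the latest date that its known parts allow, is before the treatment-emergence reference date, classify the AE as not treatment-emergent. This mirrors the medication rule.
2. Never impute an onset after the latest possible stop date, or outside the known month or year.
3. Use the first-dose date as the single anchor for every comparison, and align SAP 10.2 with the first-dose reference in Protocol 10.1.5 and 12.4.3.1.
4. Treat an onset whose known parts end before the anchor as pre-treatment. Otherwise set onset to the later of the anchor and the earliest date that the known parts allow.

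Changing SAP 10.2 alone would do harm. Wholly missing onsets, and the month-end cases sent to the catch-all, would still be dated Day 0 and would then fall out of the tables even when they began on treatment.

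With the stop-date check, no AE known to have ended before randomization can enter the TEAE tables, by construction. The single anchor removes the month-end overlap and gap. The cost is a few lines of SAP text and code, plus a small change in which Day 0 events count: an AE that starts after randomization but before first dose would no longer be treatment-emergent unless it worsens on treatment.

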#### For Concomitant Medications

Start Date: If start date is completely missing and end date is not prior to randomization, then the medication will be classified as concomitant. If start date is completely missing and end date is prior to randomization, then the medication will be classified as prior.

If (year is present and month and day are missing) or (year and day are present and month is missing) then set month and day to January 1. If year and month are present and day is missing then set day to first day of month.

End Date: If end date is completely missing then the medication will be classified as concomitant. If (year is present and month and day are missing) or (year and day are present and month is missing) then set month and day to December 31. If year and month are present and day is missing then set day to last day of the month.

Note: that if both start and end dates are missing then the medication will be classified as concomitant.

AXSOME Therapeutics, Inc. AXS-05-MDD-201 SAP CONFIDENTIAL Page 16 of 16
